Appendix XII. Critical-Care Pain Observation Tool (CPOT) developed by Gelinas et al. .35
Appendix XIII. Numeric Rating Scale (NRS).....36

Abbreviation list

ICU	Intensive care unit
IWS	Iatrogenic withdrawal syndrome
MGH	Montreal General Hospital
MUHC	McGill University Health Centre
OIWS	Opioid-associated iatrogenic withdrawal syndrome
PICU	Pediatric intensive care unit
RVH	Royal Victoria Hospital

1. Introduction

Adult medical, surgical and trauma intensive care unit (ICU) patients routinely experience pain, agitation, delirium and anxiety (1). Opioids and benzodiazepines are the primary medications to relieve pain, facilitate mechanical ventilation and decrease physiological and psychological stress in the critically ill (1). In a prospective, observational study in 51 Canadian ICUs, 92% of patients received opioids and sedatives at least once during mechanical ventilation (2). Upon repeated and prolonged administration, opioid tolerance may develop as a result of receptor desensitization and upregulation of excitatory intracellular pathways (2, 3). When these drugs are abruptly discontinued or rapidly tapered, patients may develop a cluster of signs and symptoms known as the acute iatrogenic withdrawal syndrome (IWS). While this phenomenon is well described in the pediatric critical care population, there is a paucity of data in critically ill adults (4-7). IWS has been associated with negative clinical outcomes such as increased length of hospital stays, prolonged duration of mechanical ventilation and higher cost of hospitalization (4-7).

In one prospective, observational study, the reported incidence of IWS in the adult ICU population was 16.7% (8). In prospective studies done in the pediatric ICU (PICU), observed incidence was 7.5 to 100% (9). Two assessment tools have been validated in children: The Withdrawal Assessment Tool-Version 1 (WAT-1) and the Sophia Observation Withdrawal Symptoms-scale (SOS) (10). No such tool currently exists in the adult ICU (9).

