Identifying IWS can be challenging in the critically ill. Several confounding factors (delirium, worsening of critical illness, presence of multiple agents with potential to cause withdrawal, comorbidities) may mimic symptoms similar to opioid or benzodiazepine withdrawal (6, 11). To our knowledge, no study on the symptomatology of IWS has been conducted to describe opioid or benzodiazepine withdrawal exclusively. This is most likely due to the presentation similarities of both syndromes and frequent concomitant use of these drugs in the ICU setting (4, 9).

No physiological markers have been identified to correlate with IWS. In outpatients with chronic opioid addiction, several studies have shown a significant association between increased cortisol and catecholamine levels and acute withdrawal following naloxone reversal. Cortisol and catecholamines are two stress markers that reflect the state of distress and adrenergic hyperstimulation characteristic of opioid withdrawal (12).

To date, the clinical presentation of opioid withdrawal in the adult ICU has not been characterized in a prospective setting. The present study thus aims to describe the symptomatology of opioid-associated iatrogenic withdrawal in two adult tertiary care centers in Montréal, Québec, Canada and explore the potential of using serum cortisol as a biomarker (4, 9).

2. Literature review

Research strategy can be found in Appendix I.

Epidemiology

A systematic review on the epidemiology, risk factors and symptomatology of IWS was recently conducted and identified only one prospective study on IWS in the adult ICU population, which reported an incidence of 16.7% (8, 9). In retrospective trials, incidence ranged from 19.7 to 100% (9). These heterogeneous results are likely attributed to the lack of standardized definition and evaluation of IWS (9).

Risk factors

There is significant overlap in the IWS risk factors identified in pediatric and adult populations such as younger age (3, 4, 7, 9) duration of continuous opioid therapy (i.e. more than three to five days) and prolonged benzodiazepine exposure (4, 5, 7, 9, 13-17). Additional risk factors identified specifically in the adult ICU include higher daily doses of opioids and benzodiazepines, as well as the presence of acute respiratory distress syndrome (ARDS) (7, 9). In the PICU, prolonged exposure prior to weaning

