The literature on opioid dependence has consistently demonstrated elevated levels of cortisol (12, 25-38) and catecholamines (12, 39-43) during the acute withdrawal phase. Human and animal

models postulate that long-term use of opioids induces hypoadrenalism through impairment of the hypothalamic-pituitary-adrenal (HPA) axis. Opioid withdrawal leads to marked elevations of cortisol as a result of excess ACTH secretion (26, 32, 35). This HPA activation persists following normalization of the adrenergic system, which led some authors to conclude that cortisol is a more sensitive indicator of opioid withdrawal than catecholamines (30, 32). A small study by Higgins et al. on 5 non-dependent subjects assessed acute opioid withdrawal after a single dose of morphine and observed a dose-dependent increase in cortisol levels when subjects were subsequently injected with naloxone (28). Despite the clinical relevance, several limitations reduce the applicability of those results to our study population, mainly the selection of opioid-dependent subjects and rapid induction of withdrawal – through injection of naloxone or abrupt cessation of opioid with support medications such as alpha₂-agonists. Since our subjects are mostly opioid-naive prior to hospitalization and will be gradually weaned off their opioids, the magnitude of increase in cortisol levels will likely be lower.

As for catecholamines, serum epinephrine and norepinephrine appear to increase rapidly following opioid withdrawal in numerous animal and human studies (12, 39-43). However, in contrast with cortisol, catecholamine levels decrease shortly following acute withdrawal. In a study of subjects undergoing rapid opioid detoxification, catecholamine levels peaked two hours following naloxone administration (12). A gradual opioid weaning as often seen in clinical practice is unlikely to be recognized through measurement of serum catecholamines.

3. Research objectives

Research question

What are the signs and symptoms of opioid-associated iatrogenic withdrawal syndrome (OIWS) in the adult ICU population?

Primary objective

To identify specific signs and symptoms of OIWS in mechanically ventilated adult ICU patients receiving at least 72 hours of regular opioids at the Montreal General Hospital (MGH) and the Royal Victoria Hospital (RVH) from February to October 2018

Secondary objective

To determine if the presence of OIWS is associated with an increase in serum cortisol.

4. Methods

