5.1 Statistical analysis

5.1.1 Descriptive statistics

Demographic and clinical characteristics of patients who developed OIWS will be compared to those who did not. Categorical variables will be presented as proportions. For continuous variables, means and standard deviations will be computed for normal distributions whereas medians (interquartile range) will be used for non-normal distributions.

For the primary outcome, episodes will be compared between the withdrawal positive (W+) group and the withdrawal negative (W-) group. Every day on which the DSM-5 is positive is equivalent to an episode of withdrawal, whereas a negative DSM-5 counts as an episode in which no withdrawal was observed. Patients who are positive for at least one episode of withdrawal make up the W+ group, whereas those who did not have a single episode of withdrawal make up the W- group, thus eliminating crossover. If a single patient experiences multiple days of withdrawal, s/he will account for multiple episodes in the study. Signs and symptoms will be tallied per episode and compared between the two groups. The results will be presented as proportions (i.e. incidence of symptom per total episodes). In the event of a discordant inter-rater evaluation, only the positive result will be taken into account.

For the secondary outcome, serum cortisol levels and changes in serum cortisol levels are continuous variables and therefore descriptive statistics will be used as stated above, depending on the distribution.

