5.1.2 Statistical inference

To gauge for presence of evaluation bias, inter-rater agreement will be determined using Cohen's kappa. This test measures the extent to which physicians concur when assessing for presence of OIWS using the DSM-5 criteria. A kappa of ≥ 0.61 is indicative of good inter-rater agreement (70).

For secondary outcomes, baseline, weaning and change in cortisol levels will be compared between patients positive and negative for OIWS. A Student's t-test or a Wilcoxon signed rank test will be used. The test will be determined based on distribution and sample size.

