5.2 Sample size

Based on our experience with the WAAICUP studies, 88 patients were eligible to participate in the study in an 8-month period, of which around 50 consented (22). We thus aim to recruit 50 patients based on the feasibility of these previous studies.

6. Advantages and limitations

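### For cortisol groups likely to be unbalanced, the plan's parametric option is Student's pooled t-test, whose error rate is wrong in either direction if spreads differ; prespecify Welch's test on the log scale

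*Combined protocol and SAP*

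**What the plan says.** The secondary objective (Section 3) asks whether OIWS goes with a rise in serum cortisol. Section 5.1.2 compares three quantities (baseline level, weaning level and change) between patients with and without OIWS, using a Student's "t-test or a Wilcoxon signed rank test will be used. The test will be determined based on distribution and sample size". It names no normality check, sample-size threshold, default or unequal-variance version.

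Four other places determine the group sizes:
- Section 5.2: "We thus aim to recruit 50 patients based on the feasibility of these previous studies". The earlier experience was that "88 patients were eligible to participate in the study in an 8-month period, of which around 50 consented".
- Section 1: in the one prospective adult study, "the reported incidence of IWS in the adult ICU population was 16.7" per cent. Section 2, Epidemiology, adds: "In retrospective trials, incidence ranged from 19.7 to 100" per cent.
- Section 5.1.1: "Patients who are positive for at least one episode of withdrawal make up the W+ group". On double ratings: "In the event of a discordant inter-rater evaluation, only the positive result will be taken into account". The second rule can only enlarge W+.
- Section 4.4.2: cortisol is drawn only from patients not on exogenous corticosteroids. The expected fraction is not given.

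Section 6.2 says that the sample was set by feasibility, that significant associations cannot be claimed, and that the analysis is mainly descriptive.

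**The concern.** Student's test assumes one common variance and estimates it by pooling. When one group is much smaller, the larger group dominates the pooled estimate. If the small group is the more variable, the standard error is too small and the test rejects too often. If it is the less variable, the standard error is too large and the test rejects too rarely. Equal group sizes largely protect against this; unequal sizes do not.

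Choosing the test by looking at the distribution does not help, because a normality check does not examine whether the variances are equal.

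At stake is the p-value, and any interval reported with it, for the only between-group test that the plan names. Section 6.1 presents cortisol as a new and exploratory line of research, so a miscalibrated result could mislead whoever decides whether to pursue it.

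**Working it through.** **No figure to reproduce.** The target of 50 rests on feasibility. The plan states no alpha, power, effect size, SD or group split for cortisol. Alpha is taken below as two-sided 5%.

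**Group sizes (inferred).** 0.167 × 50 = 8.35, so about 8 v 42 if all 50 give cortisol. The 95% range of a binomial (50, 0.167) is 4 to 14 positives. If only 35 or 30 patients are off steroids (assumed), 0.167 × 35 = 5.8 and 0.167 × 30 = 5.0, giving about 6 v 29 or 5 v 25. At 19.7% incidence, 0.197 × 50 = 9.85, or about 10 v 40.

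**Why pooling fails.** Set the W- SD to 1 and the W+ SD to r, at 8 v 42.
- Pooled variance on average = (7r² + 41)/48; SE used = √[pooled variance × (1/8 + 1/42)].
- True SE = √(r²/8 + 1/42).
- r = 2: pooled variance 69/48 = 1.4375; SE used √(1.4375 × 0.1488) = 0.46; true SE √0.5238 = 0.72. The SE used is 0.64 of the true one.
- r = 0.5: pooled variance 42.75/48 = 0.8906; SE used √(0.8906 × 0.1488) = 0.36; true SE √0.0551 = 0.23. The SE used is 1.55 times the true one.

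**Simulated error rate** (normal data, equal means, nominal 5%; 40,000 data sets per cell for the t-tests, 10,000 for rank-sum):

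| W+/W- SD ratio (assumed) | Student, 8 v 42 | Welch, 8 v 42 | Rank-sum, 8 v 42 | Student, 5 v 25 | Student, 25 v 25 |
|---|---|---|---|---|---|
| 0.5 | 0.3% | 5.0% | 1.0% | 0.4% | 5.3% |
| 1 | 5.1% | 5.4% | 4.6% | 5.0% | 5.1% |
| 1.5 | 13.0% | 4.9% | 8.4% | 13.2% | 5.1% |
| 2 | 20.7% | 5.1% | 11.3% | 20.7% | 5.1% |
| 3 | 29.7% | 5.0% | 13.9% | 30.3% | 5.3% |

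At 14 v 36, the top of the binomial range, Student's error is about 10% to 18% for ratios 1.5 to 3, and Welch's is about 5%. The 25 v 25 column shows that imbalance together with unequal spread is the cause.

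**Does choosing the test by distribution help?** One reading of the rule, assumed because the plan names no check, is Shapiro-Wilk at 5% in both groups, then Student's test if both pass and rank-sum otherwise. On normal data at 8 v 42 the overall error is 13.7%, 20.7% and 28.6% at ratios 1.5, 2 and 3. That is close to always using Student's test.

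**Which scale?** With identical log-normal groups at 8 v 42 (log SD 0.3 to 1.0), Student's error on raw values is 4.7–4.9% but Welch's is 6.0–10.2%. On log values Welch returns to about 5%. The remedy therefore needs the log scale as well as Welch.

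**The case against.** Five points can be made for the plan.

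**The rule might not pick Student's test.** A reader might infer that a distribution check on about 8 values would miss skew and so usually default to Student's test. The documents do not support this. The rule also cites sample size, which could send a small group to the rank test, and nothing limits the check to the smaller group. At log SD 0.5, Shapiro-Wilk rejects about 19% of the time at n = 8 but 86% at n = 42, so if both groups must pass, the t-test is kept only about 11% of the time. Change is less skewed: with an assumed correlation of 0.5 between the two levels, both groups pass in 78%, 53% and 27% of runs at log SD 0.3, 0.5 and 0.7. Student's branch is thus a real possibility for change, but not a certainty.

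**The direction is unknown.** A reader might infer a false-positive cortisol signal, because Section 2, Biomarkers, reports that "Opioid withdrawal leads to marked elevations of cortisol as a result of excess ACTH secretion (26, 32, 35"). The same paragraph expects a smaller rise here, in mostly opioid-naive patients weaned gradually. Real elevations in W+ would also raise its mean, so rejection would not then be a false signal. Nor do they imply unequal spread at baseline, sampled around the start of weaning.

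**The split is not stated.** 8 v 42 should not be read as a fact of the plan. Retrospective incidences are higher, and counting discordant ratings as positive enlarges W+. At 20 v 30 and ratio 1.5, Student's error is only 6.9%.

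**Skew alone does not harm Student's test**, as the identical log-normal groups show. This stands, and it is why the log scale matters.

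**The stakes are limited.** Cortisol is secondary and exploratory, and Section 6.2 disclaims significance. This lowers the importance, but Section 5.1.2 still prescribes tests and their results will be read.

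**Conclusion.** The point holds as a weakness of specification. The plan's only parametric option assumes equal variances in groups that are probably unbalanced, and the rule for choosing the test does nothing about unequal spread. If spreads differ, the true error of a nominal 5% test could lie anywhere from about 0.3% to 30% at 8 v 42, over assumed SD ratios of 0.5 to 3. If spreads are equal there is no error, and the problem shrinks as the groups approach equal size. These figures rest on normal data, a two-sided 5% level, assumed SD ratios, and 16.7% incidence applied to 50 patients. The documents support neither a predicted direction nor a claim that Student's test will usually be the one used. The change should be made because it is nearly free, but it concerns an exploratory secondary outcome and leaves the primary description of symptoms untouched.

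**What to change.** In Section 5.1.2:
- Delete the rule that chooses the test from distribution and sample size.
- Prespecify Welch's unequal-variance test with a 95% interval, on log cortisol for the baseline and weaning levels.
- For change, use the difference of logs (log weaning minus log baseline), back-transformed and reported as a ratio. Amend the definition of change in Section 4.4.2 to match; a raw difference can be negative and cannot be logged.
- Remove the signed rank test. It needs paired observations, and W+ and W- are different patients. If a rank method is wanted as a supplement, the independent-groups version is the rank-sum test. It is not a cure for unequal spread, as its column in the table shows.
- State how many patients in each group contribute cortisol.

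The cost is wording only, with no change to sampling or data collection. If the spreads are in fact equal, the interval is somewhat wider and power falls by up to about 6–7 percentage points. Change is also expressed as a ratio rather than an absolute difference; the raw values can still be described as Section 5.1.1 plans.

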5.2 Sample size

Based on our experience with the WAAICUP studies, 88 patients were eligible to participate in the study in an 8-month period, of which around 50 consented (22). We thus aim to recruit 50 patients based on the feasibility of these previous studies.

6. Advantages and limitations

6.1 Advantages

As stated previously, a prospective approach will limit missing data and enable assessment of potential confounders. The multicentric design enables study of different ICU populations, thereby increasing external validity and sample size.

There is currently no validated tool for OIWS diagnosis in the adult ICU population. Use of the DSM-5 is adequate in this study since it standardizes physician evaluation and is considered a gold standard in numerous settings. Multiple other ICU-validated tools will be used throughout the study such as the RASS, CAM-ICU and CPOT. Validated tools will also be used after transfer to the ward.

Training will be provided to investigators in order to standardize assessment and reduce observer bias. Observer bias will also be minimized by the blinding of investigators to DSM-5 results. Additionally, DSM-5 inter-rater agreement will be assessed on one occasion for each patient. A notable advantage is the supplemental follow-up after transfer to ward, which increases internal validity by limiting loss of patients who might develop OIWS later once transferred out of the ICU.

To our knowledge, no previous study has explored potential biomarkers that correlate with symptoms of OIWS. The exploratory use of serum cortisol in this study is thus a novel research avenue and will enable further characterization of OIWS.

6.2 Limitations

The study is susceptible to several limitations, most of them due to study design. Due to lack of randomization, the study is subject to confounding. A notable covariate is the concomitant administration of benzodiazepines, which is difficult to control for since ICU patients frequently receive both opioids and benzodiazepines, and there is significant overlap in their respective withdrawal symptoms. However, administration of benzodiazepines will be noted during daily evaluations. The study is also susceptible to the "clinical trial effect" bias, since the attending physicians are not blinded to patient enrollment in the study and may modify their management consequently. To control for observer bias, pre-tested standardized data collection forms will be used, but it does not eliminate it completely, as evaluations will be performed by different investigators.

Since the sample size was determined on the basis of feasibility rather than statistical power, no statistically significant associations can be made. Statistical analyses will thus be predominantly descriptive in nature.

The exclusion of patients with severe or moderate traumatic brain injury requiring ICP monitoring and osmotherapy reduces external validity. These patients are important consumers of opioids and are therefore at risk of developing OIWS. However, their clinical condition would make the adequate assessment of OIWS impossible.

7. Relevance of study

To our knowledge, this is the first prospective study that aims to describe the clinical presentation of OIWS in the adult ICU setting with a standardized approach, fulfilling an identified research gap (71). As mentioned, OIWS is a clinical entity associated with negative outcomes that is poorly understood in critically ill adults because of diagnostic challenges. With a more accurate description of the clinical presentation, it would be possible to develop reliable screening tools to identify patients most at risk of OIWS and to sensitize the clinician to adopt appropriate measures in their management. An accurate description of the clinical presentation of OIWS is the first step in a series of research advances aimed at correctly recognizing and managing OIWS in adult ICU patients.

8. Ethical considerations and patient consent

The study protocol will be approved by the MUHC Research Ethics Board prior to enrollment. The study procedure does not require direct medical intervention as it is observational in design. The evaluation of signs and symptoms will mostly be done using ICU standard of care assessment tools (e.g. CAM-ICU, CPOT, RASS). Assessments that are not part of routine ICU care include collection of two blood samples per patient for serum cortisol measurement and DSM-5. Investigators will not interfere with usual care, which prevents patient exposure to additional risk.

Written and informed consent will be obtained prior to enrollment and a copy will be given to the patient. Consent forms will be available in English and French with detailed descriptions of the study procedure and interventions. If the patient is inapt, consent will be obtained from a legal representative (e.g. family member). Once the patient is apt, direct consent will be sought. If the

patient refuses consent, previously collected data will be destroyed. Patients or their legal representative may decide to withdraw from the study at any moment.

Patient confidentiality will be maintained throughout the study by various means. All data will be de-identified and coded. The code will be maintained by the principle investigator. Computers and files will be password protected. Paper data will be kept in opaque envelopes in a locked cabinet to which only the investigators will have access. Study data will be kept for 7 years and the study itself will be registered on clinicaltrials.gov.

9. References

3. Best KMPRN, Wypij DP, Asaro LAMS, Curley MAQPRNF, for the Randomized Evaluation of Sedation Titration For Respiratory Failure Study I. Patient, Process, and System Predictors of Iatrogenic Withdrawal Syndrome in Critically Ill Children*. *Critical Care Medicine*. 2017;45(1):e7-e15.

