 - Agent (qualitative nominal) will be noted according to patient, family or medical chart
 - A prior history of substance abuse may render those patients more susceptible to CNS depressants (e.g. opioids and benzodiazepines)

Confounding variables

- **Chronic or occasional use of benzodiazepines prior to ICU admission** (qualitative nominal - dichotomous)
 - Agent (qualitative nominal) and total daily doses in lorazepam equivalents (mg/kg/day) (quantitative continuous) will be noted according to medication reconciliation chart at admission
 - Withdrawal due to benzodiazepines may overlap with OIWS assessment (6, 24)
- **Concomitant administration of benzodiazepines during ICU stay** (qualitative nominal - dichotomous)
 - Agent and total daily dose (mg/kg) will be noted daily (qualitative nominal and quantitative continuous, respectively), as well as total cumulative benzodiazepine dose received since ICU admission in lorazepam equivalents (mg/kg) (quantitative continuous), according to MAR.
 - Higher mean daily doses of benzodiazepines have been associated with an increased risk of IWS in ICU patients (7)
 - Withdrawal due to benzodiazepines may overlap with OIWS assessment (6, 24)
- **Administration of medication that may influence severity of OIWS** (e.g. clonidine, dexmedetomidine, methadone, buprenorphine, propofol, beta-blockers and antipsychotics) (qualitative nominal - dichotomous)
 - Agent, total daily dose will be noted daily according to MAR (qualitative nominal)
 - Clonidine, dexmedetomidine, methadone, buprenorphine and antipsychotics can be used to treat or attenuate symptoms of opioid withdrawal and therefore may confound OIWS assessment (4, 50)
- **Presence of chronic neurological conditions** (e.g. dementia, Parkinson's disease, essential tremor) (qualitative nominal - dichotomous)
 - According to past medical history in medical chart
 - Symptoms of dementia and Parkinson's disease may confound OIWS assessment
- **Presence of delirium** (qualitative nominal - dichotomous)
 - During ICU stay: according to the Confusion Assessment Method for the ICU (CAM-ICU) as measured by investigators during evaluation and/or nursing staff, collected daily once opioid weaning is initiated and until transfer
 - After transfer to ward: according to the Confusion Assessment Method (CAM) measured once by investigators within 24-96 hours of transfer
 - Symptoms of delirium may overlap with OIWS assessment (10, 20, 51)

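### Benzodiazepine exposure, delirium and pain are recorded daily as confounders, but no planned comparison of signs uses them, so the crude contrast cannot show which signs are specific to OIWS

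*Combined protocol and SAP*

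**What the plan says.** Under the confounding variables of section 4.4.1, the protocol lists benzodiazepine use before and during the ICU stay, delirium (CAM-ICU in the ICU, CAM once on the ward) and pain (CPOT or NRS above a cut-off). For benzodiazepines the stated reason is "Withdrawal due to benzodiazepines may overlap with OIWS assessment"; similar reasons are given for delirium and pain. In the ICU, benzodiazepine doses are noted daily, and delirium and pain are collected daily once weaning starts.

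Section 6.1 counts this as a strength: "a prospective approach will limit missing data and enable assessment of potential confounders".

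Section 5.1 is the whole analysis plan. For the primary outcome, "Signs and symptoms will be tallied per episode and compared between the two groups". The rest is a patient-level comparison of demographic and clinical characteristics, a kappa for the paired DSM-5 ratings, and a two-group test of cortisol. No stratification, restriction, adjustment or sensitivity table by any confounder is mentioned.

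Section 6.2 concedes that benzodiazepines are hard to control for. Its only response is that "administration of benzodiazepines will be noted during daily evaluations".

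**The concern.** The primary objective in section 3 is to identify signs that are specific to OIWS, as a step towards a bedside screening tool (4.1). Specificity is what an unstratified contrast cannot show when other causes of the same signs may be unevenly spread between the groups. Recording those causes removes no bias unless the records are used.

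The protocol supplies both ingredients of confounding by benzodiazepines. Sections 2 and 4.4.1 cite prolonged or higher benzodiazepine exposure as a risk factor for iatrogenic withdrawal. Section 2 also lists signs common to opioid and benzodiazepine withdrawal, among them nausea, vomiting, sweating, agitation, anxiety and muscle cramps, which Appendix III tallies. The same section faults an earlier paediatric symptom study for not controlling for pain and delirium. As written, this plan repeats that omission.

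At stake is the list of signs carried forward: it could include signs of benzodiazepine withdrawal, delirium or pain, or omit genuine ones.

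**Working it through.** **The plan's own figure.** Section 5.2 states "We thus aim to recruit 50 patients based on the feasibility of these previous studies", because "88 patients were eligible to participate in the study in an 8-month period, of which around 50 consented". 50/88 = 56.8%, which agrees with that text. No alpha, power or effect size is given, so there is no sample-size formula to reproduce.

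**Expected group sizes.** The Introduction says of one prospective adult study that "the reported incidence of IWS in the adult ICU population was 16.7"%. 50 × 0.167 = 8.35, so about 8 W+ and 42 W- patients.

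**Bias in the crude tally.** Take a sign that OIWS does not affect. Let p1 and p0 be the confounder's prevalence in W+ and W- episodes, and a and b the sign's frequency with and without the confounder.

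Crude difference = [p1·a + (1 − p1)·b] − [p0·a + (1 − p0)·b] = (p1 − p0)(a − b).

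The documents give none of these four values; all those below are assumptions.

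| p1 v p0 | a / b | W+ | W- | Difference (points) |
|---|---|---|---|---|
| 60% v 30% | 60% / 20% | 0.36 + 0.08 = 44% | 0.18 + 0.14 = 32% | +12 |
| 60% v 30% | 50% / 20% | 0.30 + 0.08 = 38% | 0.15 + 0.14 = 29% | +9 |
| 30% v 60% | 60% / 20% | 32% | 44% | −12 |
| 50% v 50% | 60% / 20% | 40% | 40% | 0 |
| 60% v 50% | 40% / 20% | 32% | 30% | +2 |
| 90% v 30% | 70% / 10% | 64% | 28% | +36 |

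Within a stratum the difference is zero in every row: a v a where the confounder is present, b v b where it is absent.

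**Masking.** Suppose a real OIWS sign is 12 points more frequent in W+ in both strata (72% / 32% against 60% / 20%), and the confounder is present in 30% of W+ and 60% of W- episodes. W+ shows 0.3 × 0.72 + 0.7 × 0.32 = 44%; W- shows 0.6 × 0.60 + 0.4 × 0.20 = 44%. The crude table shows nothing.

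**What stratification can bear.** One binary factor present in 50% to 80% of W+ patients (assumed) splits 8.35 into 4.2 and 4.2 at one end, 6.7 and 1.7 at the other. Splitting on three factors at once gives 8.35/8, about 1 W+ patient per cell. Restricting to episodes with none of the three, if each is independently present in 30% to 50%, leaves the equivalent of 8.35 × 0.7³ = 2.9 down to 8.35 × 0.5³ = 1.0 W+ patients.

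**Overlap between strata and signs.** On CPOT (Appendix XII), restlessness or agitation scores 2 and resistance to passive movement scores 1. The total of 3 exceeds the cut-off of 2, so a patient with only agitation and raised muscle tone, both Appendix III signs, is classed as in pain. CAM-ICU (Appendix VIII) draws on RASS fluctuation and hyperalertness.

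**The case against.** The strongest objection is DSM-5 criterion D (Appendix IV). The physician must not diagnose opioid withdrawal from signs better explained by another condition or by withdrawal from another substance. Benzodiazepine withdrawal and delirium should thus be excluded before a day is called positive. This stands in part. It could make the confounders less common in W+ episodes, which reverses the bias. But it governs the diagnosis only: Appendix III mostly counts signs whatever their cause, with cause-excluding wording for few signs, such as sweating and seizure. Section 2 itself says the two withdrawals are hard to tell apart. Under 5.1.1 only the positive result of a discordant pair counts, so one rater's exclusion can be overridden.

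Second, the study is openly descriptive: "Since the sample size was determined on the basis of feasibility rather than statistical power, no statistically significant associations can be made". With 8 v 42 patients and a sign frequency near 50%, the 95% half-width of a crude difference is 1.96 × √(0.25/8 + 0.25/42) = 38 points, taking patients as the unit. That limits what any table can show, but imprecision does not remove bias, and the objective still asks for specific signs.

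A reader might infer that the three factors enter no comparison at all. The documents do not support that. The patient-level characteristics comparison in 5.1.1 could include them, although 4.4.1 lists them separately from the demographic and clinical variables. Such a table would show imbalance but would not separate the signs.

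**Conclusion.** The point holds as a gap between the stated objective and the analysis plan: three confounders are collected daily and no planned sign comparison uses them. Signs they cause may be credited to OIWS, and real signs may be hidden.

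A reader might go further and conclude that such signs will be reported as OIWS signs. The documents do not support that. A false excess needs the confounder to be more common in W+ episodes; no prevalence is given, and criterion D could push it the other way. Over the assumed unequal prevalences with the confounder commoner in W+, the spurious difference runs from 2 to 36 points. It is zero when prevalences are equal and changes sign when they are reversed. The figure of about 8 W+ patients rests on the single 16.7% incidence carrying over to this cohort.

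Nor would it be sound to reserve the OIWS-specific label for signs whose contrast persists on days free of all three factors. That subset holds the equivalent of about 1 to 3 W+ patients on the assumptions above. Because CPOT and CAM-ICU share content with tallied signs, it would also preferentially drop days showing agitation or raised muscle tone.

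**What to change.** In 5.1.1, keep the crude table as the main one and prespecify as exploratory:

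1. The prevalence of each confounder in W+ and W- episodes.
2. Sign counts stratified by one confounder at a time, with numbers of patients beside numbers of episodes, since one patient can contribute several. Stratify first by benzodiazepine exposure or dose reduction, derived from the recorded daily doses with a stated look-back window. Then stratify by delirium (CAM-ICU in the ICU, CAM on the ward), and by pain above the cut-offs in 4.4.1.

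Add a note that CPOT and CAM-ICU overlap with tallied signs (agitation, muscle tone), so the pain and delirium strata need cautious reading. Do not add a joint three-factor restriction or a pass/fail labelling rule.

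In 6.2, state that a sign whose difference is seen only in the crude table cannot be called specific to OIWS.

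The cost is one derived benzodiazepine variable and a few extra tables from data already being collected. The downside is small cells, so show counts without tests.
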